6.2 Per protocol (PP) population

A randomized patient will be excluded from the PP set if LTOT has been discontinued or the mean LTOT utilization during follow-up to the primary endpoint is below 20 h/day for the 24 h/day group, and below 13 h/day or above 17 h/day in the LTOT 15 h/day group. Self-reported oxygen utilization at 12 months, or if that is unavailable, at 3 months will be used for PP classification.

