7.5 Analysis of primary variable

The primary endpoint of the composite event of death or 1st hospitalization at 1 year (day 365; day 0 being the day of randomization) is analyzed with Cox's proportional hazards model. Proportional hazard assumption will be investigated using graphical diagnostics based on the Schoenfeld residuals. The results will be presented as the hazard ratio (HR) for LTOT 24h/day vs. 15h/day with 90% two-sided

confidence interval and the one-sided p-value for the hypothesis test if the lower limit exceeds 0.67 (see section 9.1) A two-sided p-value for the difference between treatments will also be presented. (OS table 10 and table 11). The ITT population will be used for primary analysis but all endpoints will be analyzed according to both the ITT and the Per Protocol (PP) principle.

Statistical significance is defined as a p-value < 0.05. As a sensitivity analysis, the primary analysis is repeated adjusting for sex and age at randomization in years. A frailty model will be performed with “center” as a random effect to account for the clustering by hospital.

Cases withdrawing from LTOT treatment are for the primary analysis handled as

- 1) Per protocol, if it is due to improved oxygenation.
- 2) Having reached endpoint, if it is due to adverse event (such as excessive nose bleeding etc.).
- 3) Censored, if it is due to cancellation of treatment for reasons other than treatment allocation or adverse events (such as starting to smoke etc.).

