7.6 Analysis of secondary variables

Hospitalizations are analyzed using Fine Gray regression [ref 1,2,3] accounting for death as competing event. All-cause mortality will be analyzed as the secondary outcome. Number of competing events will be presented for each analysis. Other secondary endpoints are analyzed using two-sided Student's t-tests for continuous variables (including HRQOL, breathlessness, cognition, fatigue, activity, and health care usage) and chi-2 test for categorical variables (causes of death, cognition, treatment preference). Correlational analyses, including of factors predictive of the primary and secondary outcomes will be conducted using linear regression (continuous outcomes), logistic regression (categorical outcomes), and Cox and Fine-Gray regression models (time to event outcomes).

All analyses are subject to underlying conditions – if not fulfilled due to e.g. a too small sample, it will not be attempted. Analyses of secondary variables other than the ones underlined in section 4.2.2 will be performed at Region Blekinge.

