	All-cause mortality	LTOT 15h/day	xx	x.xx (x.xx-x.xx)	x.xx	x.xxx
	All-cause Hospitalization***	LTOT 15h/day	xx/xx	x.xx (x.xx-x.xx)	x.xx	x.xxx
	Mortality from respiratory disease	LTOT 15h/day	xx	x.xx (x.xx-x.xx)	x.xx	x.xxx
	Mortality from cardiovascular disease	LTOT 15h/day	xx	x.xx (x.xx-x.xx)	x.xx	x.xxx
	Hospitalization from respiratory disease***	LTOT 15h/day	xx/xx	x.xx (x.xx-x.xx)	x.xx	x.xxx
	Hospitalization from cardiovascular disease***	LTOT 15h/day	xx/xx	x.xx (x.xx-x.xx)	x.xx	x.xxx
At 1 year	All-cause mortality	LTOT 15h/day	xx	x.xx (x.xx-x.xx)	x.xx	x.xxx
	All-cause Hospitalization ***	LTOT 15h/day	xx/xx	x.xx (x.xx-x.xx)	x.xx	x.xxx
	Mortality from respiratory disease	LTOT 15h/day	xx	x.xx (x.xx-x.xx)	x.xx	x.xxx

	Mortality from cardiovascular disease	LTOT 15h/day	xx/xx	x.xx (x.xx-x.xx)	x.xx	x.xxx
	Hospitalization from respiratory disease***	LTOT 15h/day	xx/xx	x.xx (x.xx-x.xx)	x.xx	x.xxx
	Hospitalization from cardiovascular disease***	LTOT 15h/day	xx	x.xx (x.xx-x.xx)	x.xx	x.xxx

*** Hospitalizations are analyzed using Fine Gray regression accounting for death as competing event

Table 11.2 Secondary outcome (PP)

Table 11.3 Secondary outcome (Subgroup 1)

Table 11.4 Secondary outcome (Subgroup 2)

Table 11.5 Secondary outcome (Subgroup 3)

Table 11.6 Secondary outcome (Subgroup 4)

Table 11.7 Analysis of Self-reported hours of oxygen

Similar table as in 10.1

	Population	Outcome	Mean difference (95% CI)	p-value**
At 3 months	ITT	Self-reported hours of oxygen* (within 24 hours)	x.xx (x.xx-x.xx)	x.xx
	PP	Self-reported hours of oxygen* (within 24 hours)	x.xx (x.xx-x.xx)	x.xx
	Subgroup 1	Self-reported hours of oxygen* (within 24 hours)	x.xx (x.xx-x.xx)	x.xx
	Subgroup 2	Self-reported hours of oxygen* (within 24 hours)	x.xx (x.xx-x.xx)	x.xx
	Subgroup 3	Self-reported hours of oxygen* (within 24 hours)	x.xx (x.xx-x.xx)	x.xx
	Subgroup 4	Self-reported hours of oxygen* (within 24 hours)	x.xx (x.xx-x.xx)	x.xx
At 1 year	ITT	Self-reported hours of oxygen* (within 24 hours)	x.xx (x.xx-x.xx)	x.xx
	PP	Self-reported hours of oxygen* (within 24 hours)	x.xx (x.xx-x.xx)	x.xx
	Subgroup 1	Self-reported hours of oxygen* (within 24 hours)	x.xx (x.xx-x.xx)	x.xx
	Subgroup 2	Self-reported hours of oxygen* (within 24 hours)	x.xx (x.xx-x.xx)	x.xx
	Subgroup 3	Self-reported hours of oxygen* (within 24 hours)	x.xx (x.xx-x.xx)	x.xx
	Subgroup 4	Self-reported hours of oxygen* (within 24 hours)	x.xx (x.xx-x.xx)	x.xx

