* Self-reported oxygen use is defined as mean hours/day. If missing, we will use mean h/day last week, using the questionnaire at 12 months, or (if missing) 3 months. (Duration=number of hours per day)

**t-test for mean difference

Table 12 Adverse events (PP and ITT)

Table 12.1 Adverse events

This table will be constructed if there is enough data.

	LTOT 15h/day n=	LTOT 24h/day n=	Total n=
Number of patients with AE (Total number of AE)	n[n]	n[n]	n[n]
Number of patients with SAE (Total number of SAE)	n[n]	n[n]	n[n]
Number of patients with possibly related AE (Number of possibly related AE)	n[n]	n[n]	n[n]
Number of patients with probably related AE (Number of probably related AE)	n[n]	n[n]	n[n]
Number of patients with unrelated AE (Number of unrelated AE)	n[n]	n[n]	n[n]
Number of AE with maximum intensity=MILD	n	n	n
Number of AE with maximum intensity=MODERATE	n	n	n
Number of AE with maximum intensity=SEVERE	n	n	n
Number of patients with maximum AE intensity=MILD	n	n	n
Number of patients with maximum AE intensity=MODERATE	n	n	n
Number of patients with maximum AE intensity=SEVERE	n	n	n

Table 12.2 Time to adverse events

		LTOT 15h/day n=	LTOT 24h/day n=	Total n=
Time to adverse events (all adverse events)	n			
	Mean (SD)			
	Median (IQR)			
	Min-Max			

2 Figures

NOTE: All figures below are based on dummy data

Figure 1 [Figures for inclusion over time](#)

Figure 1.1 Cumulative enrollment over time in the study (all randomized patients)

[figure not shown]

Figure 1.2 Cumulative enrollment over time in the study (by treatment)

If applicable

Figure 1.3 Cumulative enrollment over time in the study (by site)

If applicable

Figure 1.4 Cumulative enrollment over time in the study (by subgroup)

If applicable

Figure 1.5 Histogram with number of included patients by site and by treatment group

[figure not shown]

Figure 1.6 Reasons why the screened patients were not included in the study

[figure not shown]

Figure 1.7 Kaplan-Meier figure: Time from start until the patient stops being treated

A figure will be constructed and presented by treatment arm. Patients who stop being treated with oxygen before one year will be censored at this time.

Figure 2 CONSORT flow chart

* A patient is correctly randomized if he or she fulfills the inclusion criteria but not the exclusion criteria, has signed informed consent and has been randomized in Swedevox within four weeks of starting LTOT.

**All registry data available except for withdrawals

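### The PP rows of Table 11.7 test reported oxygen hours between arms in a set selected on those hours, so they cannot show that the prescription changed use

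*SAP*

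**What the plan says.** Section 6.2 of the SAP removes a patient from the PP set if LTOT was discontinued or if mean use was "below 20 h/day for the 24 h/day group, and below 13 h/day or above 17 h/day in the LTOT 15 h/day group". The source is stated: "Self-reported oxygen utilization at 12 months, or if that is unavailable, at 3 months will be used for PP classification".

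Section 4.1.2 lists reported oxygen use as a secondary objective. Section 1 does not place it among the objectives left to the sponsor, so it is due in the main study report. Table 11.7 in Appendix 2, "Analysis of Self-reported hours of oxygen", gives a mean difference, 95% CI and p-value for ITT, PP and four subgroups, at 3 months and again at 1 year. Its footnotes specify a "t-test for mean difference" and take the hours "using the questionnaire at 12 months, or (if missing) 3 months". The derived-variables list uses the same order of preference, and adds that its averaging algorithm applies at each time point.

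Section 7.6 prescribes "two-sided Student's t-tests for continuous variables", and section 7.5 sets the threshold: "Statistical significance is defined as a p-value < 0.05". The PP rows follow from the general rule in sections 6 and 7.5 that every endpoint is analysed in both ITT and PP. Nothing exempts this outcome or marks its PP rows as descriptive.

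**The concern.** Selection and outcome share one variable, one source and one fallback rule. The PP limits for the two arms do not overlap, so patients are kept because their hours already differ by arm, and the table then tests whether hours differ by arm.

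Section 6 itself notes that non-adherence pulls this trial towards equivalence. Readers of the primary result will therefore want evidence that the arms separated on oxygen use. A large difference with a very small p-value in the PP rows could be taken as that evidence, although the PP rule alone can produce it.

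**Working it through.** **The plan's own figure.** The SAP gives no expected result for Table 11.7. Its one computed figure is the sample size in section 9.2, which reproduces: (1.645 + 0.842)² / (ln(1.5)² × 0.25 × 0.8) = 188.03, rounded up to 189. It is used here only to gauge the size of the PP set: 189/2 is about 95 per arm.

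**Step 1: bounds on the difference.** Inputs from section 6.2: the 24 h arm is kept at 20 h/day or more (at most 24 is possible), and the 15 h arm at 13 to 17 h/day. If the analysed value is the classifying value:
- smallest mean difference = 20 − 17 = 3 h/day
- largest mean difference = 24 − 13 = 11 h/day

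**Step 2: smallest possible t statistic.** Take n patients per arm in both arms. Variance is greatest, and t smallest, when all values sit at the limits. Let a fraction p of each arm sit at the outer limit (24 or 13) and the rest at the inner limit (20 or 17). Then

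t = (3 + 8p) / (4√(2p(1 − p))) × √(n − 1),

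which is smallest at p = 3/14: 4.714 / 2.321 × √(n − 1) = 2.03 × √(n − 1). A search over whole-number counts at the limits gives:

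| n per arm | smallest t | two-sided p |
|---|---|---|
| 2 | 2.47 | 0.13 |
| 3 | 3.01 | 0.040 |
| 10 | 6.10 | 9 × 10⁻⁶ |
| 95 | 19.7 | about 10⁻⁴⁷ |

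No assumption about the distribution of hours is needed. With three or more per arm, p < 0.05 is certain.

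**Step 3: no true effect.** Assume hours have the same distribution in both arms: normal, mean 18, SD 4, capped at 24, with 115 per arm (230/2) and 2,000 runs. The PP rule is applied to the 12-month value and keeps about 35 and 34 patients per arm.
- PP, 12-month value: mean difference about 6.9 h/day, p < 0.05 in 100% of runs.
- ITT, 12-month value: p < 0.05 in 4.6% to 5.4% of runs, as it should be.

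**Step 4: 3-month values in a set selected on 12-month values.** Same assumptions, varying the correlation between the two reports:

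| correlation | mean difference, h/day | p < 0.05 |
|---|---|---|
| 0 | 0.0 | 4% |
| 0.2 | 1.4 | 34% |
| 0.3 | 2.0 | 62% |
| 0.5 | 3.4 | 99% |
| 0.7 | 4.8 | 100% |
| 0.9 | 6.2 | 100% |

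Here there is no 3 h floor. The false-positive rate depends on a correlation that the SAP does not give.

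**The case against.** A reader might infer that both PP rows are settled in advance. The SAP does not support that. Section 6.2 classifies on the 12-month report first, and the note in the derived-variables list about each time point suggests that the 3-month row uses 3-month values. For a patient with both forms, the 3-month value is then not the selecting value, and Step 4 shows that the outcome is open when the correlation is low. This part of the objection stands. The 3-month row is fixed only for patients without a 12-month form, or if the footnote's 12-month-first rule is applied literally to both rows.

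The 1-year row also rests on a reading. Section 7.7 keeps forms submitted after hospitalization out of the analysis of the primary outcome, and section 9.2 assumes that 80% of patients have an event. If that bar also governs PP classification, some patients would be classified on the 3-month form while their 12-month value enters Table 11.7, and the 3 h floor would fail for them. The SAP does not say whether it does. This stands as a qualification.

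The ITT row sits directly above each PP row and answers the objective without this selection. Tables 1 and 2 would show low adherence. Both points are true and limit the harm, but neither makes the PP test informative.

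**Conclusion.** The point holds with limits. Where the analysed report is the classifying report, the PP comparison must show 3 to 11 h/day and is significant from three patients per arm (equal arms) by arithmetic alone. On the plain reading that is the 1-year row, plus the 3-month values of patients without a 12-month form. Elsewhere the comparison is biased by selection to a degree that depends on the correlation between reports. The simulated rates rest on the assumed mean of 18, SD of 4 and correlations; the bounds and smallest t values do not.

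It would be wrong to conclude that the primary analysis or the ITT comparison of hours is compromised. Neither is affected, and the subgroup rows are not shown as restricted to PP. The matter concerns two rows for one secondary outcome and is minor.

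**What to change.** Remove the two PP rows (mean difference, CI and p-value) from Table 11.7. Add one sentence to section 6 or 7.5 exempting reported oxygen hours from the rule that every endpoint is also analysed in PP, because the PP set is defined by those hours. Test hours in ITT and in the subgroups not restricted to PP.

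No new table is needed. Table 9.2 already describes hours in the PP set, and Tables 1 and 2 already give PP numbers and exclusion reasons by arm, which can serve as the adherence result. The cost is two deleted shell rows and one sentence, and no informative result is lost.

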4.2.2 Secondary outcome variables

- Mortality rate from all causes at 3 and 12 months
- Mortality rate from respiratory disease at 3 and 12 months
- Mortality rate from cardiovascular disease at 3 and 12 months
- Hospitalization rate from all causes at 3 and 12 months
- Hospitalization rate with a primary diagnosis of respiratory disease or respiratory infection at 3 and 12 months
- Hospitalization rate with a primary diagnosis of cardiovascular disease at 3 and 12 months
- Rate of an incident diagnosis of cardiovascular disease at 3 and 12 months

Self-reported questionnaire data collected at 3 and 12 months:

- Self-rated oxygen utilization
- Breathlessness (Multidimensional Dyspnea Profile; MDP)
- Fatigue (FACIT-Fatigue)
- Informant-rated cognition (IQCODE and FAQ)
- Self-rated cognition (BAS)
- Health-related quality of life (CAT and EQ5D-5L)
- Global impression of change from baseline (GIC)
- Self-reported physical activity
- Preference of continuing treatment

5 Study design

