7.7 Handling of missing data and data outside range

No imputation of missing data for variables used in the primary or secondary analyses will be performed. Only observed data will be used in the analyses.

If the date on a 3-month or 12-month form is either missing or unreadable we assume that the form was filled out at exactly 3 months or 12 months, respectively. For the PP analysis of the primary endpoint, the 3-month observation of self-reported oxygen utilization will be used if the 12-month observation is missing.

Data from forms submitted after hospitalization will not be used in the analysis of the primary outcome.

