*Socialstyrelsen will provide us with the date of event. Time to event (in days) will be calculated by UCR

*Time to composite event (All-cause mortality/ All-cause Hospitalization)	Included in the order from Socialstyrelsen
*Time to all-cause mortality	Included in the order from Socialstyrelsen
*Time to 1st hospitalization	Included in the order from Socialstyrelsen
Mortality from respiratory disease	respiratory disease or infection (A40; J00-J99)
Mortality from cardiovascular disease	Underlying cause of death (UCD) heart disease (I00-I99)
Hospitalization from respiratory disease	UCD respiratory disease or infection (A40; J00-J99)
Hospitalization from cardiovascular disease	UCD heart disease (I00-I99)
Time to Mortality from respiratory disease	Death (from respiratory disease) date – Study start date
Time to Mortality from cardiovascular disease	Death (from cardiovascular disease) date – Study start date
Time to Hospitalization from respiratory disease	Date of hospitalization from respiratory disease – Study start date
Time to Hospitalization from cardiovascular disease	Date of hospitalization from cardiovascular disease – Study start date
Time from start until the patient stops being treated	End of treatment – Date for start of treatment
Discontinued LTOT	From Swedevox Registry
Withdrawals	DATE_OF_LTOT_WITHDRAWAL REASON_W
ITT	All randomized patients that start LTOT
PP	A randomized patient will be excluded from the PP set if LTOT has been discontinued before the primary outcome assessment or the mean LTOT utilization during follow-up to the primary endpoint is below 20 h/day for the 24 h/day group, and below 13 h/day or above 17 h/day in the LTOT 15 h/day group
COPD	J44; exacerbation: J44.0 and J44.1
Heart disease	I00-I99
Respiratory disease or infection	A40; J00-J99
fev1/fvc	FEV1/FVC
BMI	WEIGHT(kg)/(HEIGHT (m)*HEIGHT (m))
Age	Round down (RANDOMIZATION_DATE - DATE_OF_BIRTH)/365.25
Duration of treatment	Number of days with treatment during the study
Self-rated hours of oxygen	Self-reported oxygen use (mean hours/24h) is categorized using 1) average use since starting LTOT, or (if missing) mean h/day last week; using the

	questionnaire at 12 months, or (if missing) 3 months (and the described algorithm used for each time point).
Subgroup 1 Participants with more severe resting hypoxemia at LTOT start	PaO ₂ < 7.4 kPa breathing air
Subgroup 2 Participants with more moderate hypoxemia at LTOT start	PaO ₂ 7.4–8.0 kPa breathing air

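### The oxygen-hours footnotes let 3-month answers stand in the 1-year row of a secondary outcome, which conflicts with the missing-data rule in SAP 7.7

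*SAP*

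**What the plan says.** SAP 4.2.2 lists self-rated oxygen utilization among the secondary outcomes, under "Self-reported questionnaire data collected at 3 and 12 months". The related objective is not among those that section 1 leaves to the sponsor. Output-shell Table 9.1 has one oxygen-hours row at 3 months and one at 12 months. Table 11.7 tests the mean difference by t-test in ITT, PP and four subgroups, at 3 months and again at 1 year: 12 tests.

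All these rows carry the same asterisk. The footnote first defines oxygen use as mean hours per day and then continues: "If missing, we will use mean h/day last week, using the questionnaire at 12 months, or (if missing) 3 months". It has no rule specific to a row. The derived-variables entry for self-rated hours gives the same order of questionnaires and adds in brackets "and the described algorithm used for each time point", a remark that neither footnote repeats.

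The body of the SAP is narrower. Section 7.7 says "No imputation of missing data for variables used in the primary or secondary analyses will be performed" and "Only observed data will be used in the analyses". It then makes one provision for oxygen hours, repeated in 7.4: "For the PP analysis of the primary endpoint, the 3-month observation of self-reported oxygen utilization will be used if the 12-month observation is missing". Section 6.2 uses the same order to sort patients into the PP set: "Self-reported oxygen utilization at 12 months, or if that is unavailable, at 3 months will be used for PP classification".

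**The concern.** The footnotes take a rule that the body of the SAP sets up for PP classification, where one value per patient is needed, and attach it to an outcome reported and tested at two separate times. A programmer who follows the shell would put 3-month answers into the 1-year row, contrary to 7.7.

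Section 6 warns that non-adherence may bias the comparison towards equivalence. In a non-superiority trial, the difference between the arms in hours used is the evidence that 24 h and 15 h per day were in fact compared. Section 5.4.3 sends questionnaires only to patients still alive, so the values carried forward come from patients who died between the two mailings or stopped answering. The 1-year mean, its patient count and its p-value would then describe a mixture of times under a single label. The SAP gives no basis for saying which way the estimated difference would move.

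**Working it through.** The SAP states no figure for this point, so there is none to reproduce. The check has two parts.

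**1. What the rule does to the rows.** The hours here (15 at 3 months, 20 at 12 months) are illustrative.

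Broad reading: the questionnaire order governs the whole definition, so value = 12-month answer, otherwise 3-month answer, in every row with the asterisk.

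| Answers (3 mo, 12 mo) | Footnote: 3-mo row, 1-yr row | Own form only: 3-mo row, 1-yr row |
|---|---|---|
| 15, 20 | 20, 20 | 15, 20 |
| 15, missing | 15, 15 | 15, missing |
| missing, 20 | 20, 20 | missing, 20 |
| both missing | missing, missing | missing, missing |

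Narrow reading: the questionnaire order governs only the fallback to the last-week item. A patient who gives average use on both forms then contributes 15 and 20, as intended. A patient without a 12-month form still receives the 3-month last-week answer in the 1-year row. The rows differ, but 3-month values still enter the later one.

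On both readings, the second pattern breaks 7.7.

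**2. How many values could be affected.** The planned size of 230 is in SAP 9.2. Mortality (10% by 3 months, 30% by 12 months) and response among the living (60–90%, the same rate r at both times) are assumptions. Every returned 3-month form is taken to hold a usable answer.

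- Alive at 3 months: 0.90 × 230 = 207. Alive at 12 months: 0.70 × 230 = 161. Deaths in between: 46.
- Genuine 12-month values: 161r.
- Nested responders (everyone who answers at 12 months also answered at 3): carried = 207r − 161r = 46r. Share = 46r / 207r = 22% for any r.
- Independent responders: carried = 161r(1 − r) + 46r.
  - r = 0.6: 38.6 + 27.6 = 66.2 carried; row = 96.6 + 66.2 = 162.8; share 41%.
  - r = 0.9: 14.5 + 41.4 = 55.9 carried; row = 144.9 + 55.9 = 200.8; share 28%.
- Between these, with 75% response at 3 months and 70% at 12: about 155 and 113 forms. If 100 patients return both, 55 of 168 values are carried, or 33%.

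The range of 22–41% depends on similar response at the two times. If response fell from 90% to 60% with nested responders, the share would be (186.3 − 96.6) / 186.3 = 48%.

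**The case against.** The best defence is that the authors plainly meant two separate measurements. The outcome is listed as collected at both times, the tables have separate blocks, and the bracketed remark in the derived-variables entry says that the algorithm runs at each time point. That entry also speaks of categorizing use, which suggests a PP rule copied into the footnotes by accident. An analyst would hardly fill a 3-month row from 12-month forms.

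Much of this stands. A reader might infer from the footnote that the two rows are bound to be the same variable. The documents do not support that as the only meaning: it follows on the broad reading but not on the narrow one, and the bracketed remark leaves the intent open. That remark does not settle the matter, however. It may mean only that the choice between average use and last week is made within each questionnaire, it stands beside the 12-then-3-month order without cancelling it, and it is missing from the footnotes.

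A reader might also infer that the fallback would conceal a fading difference between the arms. That is too strong. The first-choice item is average use since LTOT began, a cumulative figure that smooths late change even if every 12-month form comes back.

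It can also be said that a 3-month answer is observed data and so not imputed. But 7.7 itself treats this substitution as a missing-data provision and ties it to the PP analysis of the primary endpoint.

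**Conclusion.** The conflict is real and of moderate weight. The footnotes to Tables 9.1 and 11.7, with the derived-variables entry, extend to a tested secondary outcome a substitution that 7.4 and 7.7 provide for the PP analysis of the primary endpoint. On either reading, the 1-year row can contain 3-month values. Only on the broadest reading do the two rows coincide.

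The number affected cannot be derived from the SAP. The 22–41% rests on assumed mortality, an assumed common response rate and the assumed overlap of responders. It shows that the share need not be trivial, and it is not a forecast.

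The consequence is confined to the oxygen-hours rows of Tables 9 and 11.7. The ITT primary hazard ratio does not use these values, and PP classification follows its own rule in 6.2.

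**What to change.** In Tables 9.1 to 9.6 and 11.7, take oxygen hours only from the questionnaire of the row's own time point: average use since starting LTOT or, if that item is blank, mean hours per day in the last week from the same form. If the form for that time point was not returned, the value is missing in that row.

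Split the derived-variables entry into three: hours at 3 months, hours at 12 months, and hours for PP classification (12-month value, otherwise 3-month value). State in that entry and in both footnotes that the fallback across questionnaires serves PP classification only. Sections 6.2, 7.4 and 7.7 can stay as they are.

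The cost is two footnotes and one derivation entry, with no new data. The 1-year row will have fewer patients. On the assumptions above it would hold 161r, about 97 to 145, against about 124 to 186 with the fallback and nested responders, or 163 to 201 with independent ones.

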Summary table of abbreviations and definitions used in this plan

AE	Adverse event
COPD	Chronic obstructive pulmonary disease
DV	Derived variables
EVF	Erythrocyte volume fraction
FEV ₁	Forced expired volume in one second
VC	Vital capacity
ITT	Intention-to-treat – all randomized patients who has started LTOT, regardless of adherence (see section 6.1 in this SAP)
IQR	The InterQuartile Range (the second and third quartiles, or the middle half of the data set)
kPa	Kilopascal
LPO	Last patient out
LTOT	Long-term oxygen therapy
OS	Output shells
PaO ₂	Partial pressure of arterial oxygen
PP	Per protocol – patients who fulfill certain criteria (see section 6.2 in this SAP)

R-RCT	Registry-based, randomized, controlled trial
SAE	Serious adverse event
Safety population	All randomized patients who have started LTOT. This includes incorrectly randomized patients.
SAP	Statistical analysis plan
SD	Standard deviation
SUSAR	Suspected unexpected serious adverse reaction
Swedevox	Swedish register for respiratory failure
UCR	Uppsala Clinical Research centre

4 Study objectives and outcome variables

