6.1 Intention to treat (ITT) population

A randomized patient will only be excluded from the analysis ITT set if LTOT was never started.

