6.3 Safety population

All randomized patients who have started treatment with long-term oxygen therapy (LTOT) belong to the *Safety population* and will be studied with regard to adverse events. If there are no incorrectly randomized patients or patients who started the wrong treatment, the safety population will be the same as the ITT population.

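### The adverse-event tables are laid out for the PP and ITT sets, not the Safety population that SAP section 6.3 assigns, and the PP version is selected on tolerating treatment

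*SAP*

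**What the plan says.** Section 6.3 places every randomized patient who started LTOT in the Safety population and says this set "will be studied with regard to adverse events". The definitions in section 3 add who is in it: "All randomized patients who have started LTOT. This includes incorrectly randomized patients". On its relation to ITT, section 6.3 says: "If there are no incorrectly randomized patients or patients who started the wrong treatment, the safety population will be the same as the ITT population". Section 6.1 defines ITT by a single exclusion: "A randomized patient will only be excluded from the analysis ITT set if LTOT was never started".

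The output shells differ. Table 12 is headed "Adverse events (PP and ITT", and the contents list of Appendix 2 repeats that heading. Section 7.8, on the evaluation of safety, plans a listing and, where applicable, a frequency table by treatment group, but names no population. In the shells the Safety population appears only in Table 1, as a count with a footnote.

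On PP, section 6.2 says: "A randomized patient will be excluded from the PP set if LTOT has been discontinued". It makes no exception by reason. It also excludes patients whose mean use is below 20 h/day in the 24 h arm, or below 13 or above 17 h/day in the 15 h arm. The derived-variables appendix words the discontinuation rule differently: it applies only to discontinuation that precedes assessment of the primary outcome.

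**The concern.** A programmer works from the shell. As written, the shell yields one adverse-event table on ITT and one on PP, and none labelled with the set that the SAP defines for safety.

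The PP table is the more serious part, because membership of PP depends on tolerating the treatment. Section 7.5 expects some patients to withdraw from LTOT because of an adverse event and gives nose bleeding as an example. Section 6.2 then takes such a patient out of PP, and with them the event that made them stop. The trial compares two treatment burdens, so tolerability by arm will be read closely. A by-arm table that tends to drop treatment-limiting events may look more balanced, or more benign, than the randomized groups were.

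**Working it through.** The SAP gives no figure for this point, so the check is to set the definitions side by side and follow types of patient through them.

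**Safety against ITT.** Both sets require randomization and a start of LTOT. Section 6.3 names two exceptions to their being the same:

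- Incorrectly randomized patients. Section 3 puts them in Safety. Whether they are in ITT is less clear. Section 6.1 would keep them if they started LTOT, but section 3 describes the group of all randomized patients as those who met the eligibility criteria.
- Patients who started the wrong treatment. They did start LTOT, so they meet both membership rules. The difference can only be the arm under which they are counted, and the SAP does not state that.

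If neither type occurs, the ITT version of Table 12 is the Safety table under another name.

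**Safety against PP.** Patients with an adverse event, all of whom started LTOT:

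| Patient | Safety | ITT | PP by section 6.2 | PP by derived variables |
|---|---|---|---|---|
| Continues, hours within limits | in | in | in | in |
| Stops LTOT because of the event | in | in | out | out, or possibly in (see below) |
| Cuts mean hours below the arm's limit | in | in | out | out |

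The uncertain cell depends on what assessment of the primary outcome means. If it means the one-year time point, a patient who stops earlier is out. If it means the patient's own first event, someone who stops after a first hospitalization may stay in. So might someone whose withdrawal for an adverse event is itself counted as the endpoint under section 7.5. The two PP definitions need reconciling in any case.

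**The hours limits also act unequally by arm.** Measured from the prescribed hours, a patient leaves PP after cutting down by more than 24 − 20 = 4 h/day in the 24 h arm, but by more than 15 − 13 = 2 h/day in the 15 h arm. The selection rule therefore differs between the columns being compared.

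**Where the events still appear.** The ITT version of Table 12 keeps every patient in the table above. Table 1 gives LTOT discontinuations with reasons by arm, on randomized patients. Section 7.4 reports reasons for not completing randomized treatment in ITT. Listing 5 covers discontinuations and Listing 9 adverse events, and the listing in section 7.8 carries no PP restriction.

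**The case against.** The strongest reply is that little is at stake. Outside the two exceptions in section 6.3, ITT and Safety have the same members, so the table that section 6.3 calls for will be produced with a different label. PP does not stand alone, since the heading names both sets, and a reader who wants treatment-limiting events can find them in the ITT version, Table 1 and the listings. This stands, and it is why the point is minor.

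It could also be said that section 6 asks for both ITT and PP throughout. That does not stand for safety. Section 6 refers to endpoints, and its reason is that non-adherence could bias the comparison towards equivalence. It offers no reason to count adverse events in a set selected on adherence.

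A further worry is that Table 12.1 is conditional, with no criterion: "This table will be constructed if there is enough data". Adverse events are collected only at ordinary clinic visits, so sparse data are foreseeable, and section 7.8 plans the listing unconditionally. Table 12.2 carries no such condition. Producing Table 12.1 regardless of counts is a reporting preference and does not carry this point.

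**Conclusion.** The contradiction between section 6.3 and the Table 12 shell is real and should be removed. Its consequence is a misassigned analysis set and an extra table that would mislead if read as a safety comparison. It is of minor severity and does not affect the primary analysis.

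The size cannot be derived, because the SAP gives no expected number of adverse events or of withdrawals caused by them. Three stronger readings are tempting, and the document does not support them:

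- A reader might infer that treatment-limiting events disappear from the report. They do not; the ITT version, Table 1 and Listings 5 and 9 keep them.
- A reader might infer that every patient who stopped for an adverse event is absent from the PP table. That follows from section 6.2 read literally, but the derived-variables wording may keep some.
- A reader might take the sample-size margin, 230 − 189 = 41 patients (41/230 = 17.8%), as the scale of the loss. Section 9.2 allows that margin for PP losses as a whole, which include use outside the hours limits for any reason, so it does not measure withdrawals for adverse events.

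The conclusion that the PP table is selected on tolerability assumes only that some patients stop or cut down because of an adverse event. Section 7.5 already provides for patients who stop.

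**What to change.** Head Tables 12.1 and 12.2 with the Safety population, correct the contents entry in Appendix 2, and name that set in section 7.8. Delete the PP version, or label it supplementary with a note that PP excludes patients who discontinued or were outside the hours limits. State whether a patient who started the wrong treatment is counted under the allocated or the received arm. Reconcile the discontinuation wording in section 6.2 with that in the derived-variables appendix.

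Optionally, add a row to Table 12.1 for adverse events leading to LTOT withdrawal. The date and reason for withdrawal are already obtained from Swedevox, and the row would partly repeat Table 1.

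The cost is a few lines of text and a shell edit. No new data are needed, and programming is reduced if the PP version is dropped.
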